5. Theory-based mechanisms of action. Covariates will include sociodemographic variables such as age, education and income level, employment, race/ethnicity, living situation, which have been previously found to be structural drivers of HIV risk. While the intervention does not target mental health or substance use, we will assess depressive symptoms using the Center for Epidemiologic Studies Depression Scale (CES-D), and anxiety symptoms will be measured with the Beck Anxiety Inventory. We will also assess alcohol use and other drugs with the AUDIT as well as the Alcohol, Smoking, and Substance Involvement Test (ASSIST) given their associations with HIV outcomes. We will also assess history/current health care engagement (i.e., HIV prevention, primary care, mental health).

Attach any unpublished instruments in the 'Other Study Documents' section of the Initial Review Submission Packet form after completing the study application. Published instruments should NOT be attached.

8.12 * BIOSPECIMEN COLLECTION: Are you drawing any blood or collecting other biosamples (e.g. tissue, buccal swabs, urine, saliva, hair, etc.) for analysis under this protocol and/or storage for future research: (REQUIRED)

Yes No

* Could this study generate genetic data that may be broadly shared (e.g., submitted to NIH in compliance with **Genomic Data Sharing (GDS)/Genome-Wide Association Studies (GWAS)** requirements): (REQUIRED)

Yes No

Please check the Resource Sharing Plan section of your funding notice. You will not be able to share the data as required by your

funding agency if the consent form doesn't include the required language.

8.13 STATISTICAL METHODS: Briefly summarize the methods and types of analyses that will be performed:

Preliminary analyses and missing data. Frequency tables for all variables and measures of central tendency and variability for continuous variables will characterize the sample and will be stratified by study arm to check for imbalances. If the intervention and control groups differ significantly at baseline on one or more covariates, we will use methods based on the Rubin causal model (e.g., propensity scores, double-robust estimation) to obtain the desired marginal effect estimates under the counterfactual assumption of balanced groups.⁸¹⁻⁸⁵ We will address incomplete data with multiple imputation (MI)⁸⁶ because MI makes the relatively mild assumption that incomplete data arise from a conditionally missing-at-random (MAR) mechanism.⁸⁷

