Auxiliary variables will be included to help meet the MAR assumption;^{88, 89} sensitivity analyses will be conducted with weighted MI to assess the MAR assumption's robustness⁹⁰ using SAS⁹¹ and Mplus.

Primary analyses to address Primary Specific Aim 1. If the CHIP intervention is successful, a lower proportion of intervention participants will engage in CR-HIV relative to control group participants following intervention exposure. Therefore, to address Specific Aim 1 we hypothesize that the odds of CR-HIV will be lower for CHIP participants than for control participants (Hypothesis 1). Our primary interest is to estimate the marginal or population-average effects of CHIP exposure on CR-HIV rather than the effect for a hypothetical average subject or couple.⁹² Moreover, within-subject and within-couple CR-HIV correlations are nuisance parameters rather than quantities of interest to be modeled explicitly. Finally, the statistical literature indicates the superior performance of generalized estimating equations (GEE) relative to generalized linear mixed models (GLMMs) for the analysis of dyadic data with categorical outcomes such as CR-HIV.⁹³ Accordingly, we will use GEE for the proposed primary analysis to test Hypothesis 1 by a planned time-averaged comparison of post-baseline measurements of CR-HIV from the intervention group with the post-baseline measures of CRHIV from the control group. Alpha (α) will be set at .05 for this planned comparison. Any additional post-hoc comparisons (e.g., paired comparisons of groups at each time point) will maintain nominal alpha of .05 through the use of simulation-based stepdown multiple comparison methods.⁹⁴ The alternating logistic regression (ALR) approach implemented in SAS PROC GENMOD will be used to address the 3-level clustering of observations within participants and participants within dyads. Though GEE estimates are consistent even if the correlation structure is misspecified, GEE's statistical efficiency improves as the working correlation structure more closely approximates the actual correlation structure;⁹⁵ therefore, various correlation structures suitable for the study's design will be considered (e.g., exchangeable; nested-1).⁹⁶ The QIC statistic will be used to select the final correlation structure.⁹⁷ Couple serostatus will be included as a covariate as required by the stratified randomized design.⁹⁸ Additional relevant covariates such as relationship length, as well as intersectionality criteria and structural drivers (e.g., age, race/ethnicity, poverty, unemployment) will be included if they improve QIC. We will use Robust Huber-White "sandwich" standard errors to obtain correct inferences even if the chosen correlation structure remains slightly misspecified.

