11.0 Sample Size and Eligibility Criteria

11.1 ENROLLMENT TARGET: How many people will you enroll:

108

If there are multiple participant groups, indicate how many people will be in each group:

Control condition: 54 participants / 27 dyads

11.3 SAMPLE SIZE JUSTIFICATION: Explain how and why the number of people was chosen. For multi-site studies, this is referring to the number that will be enrolled across all sites:

Power analyses were generated using the two-group repeated proportions module in NCSS PASS 15104 to compute minimum detectable effect sizes for the primary analysis to address Hypothesis 1. Our pilot study found standardized effect sizes ranging from .38 to .42,¹⁶ so we powered our study to detect similarly-sized effects in worst-case scenarios where within-participant clustering of outcomes are substantial. The study will begin with 200 participants from 100 couples evenly assigned to the intervention and control groups. Assuming 20% attrition, data from 160 participants from 80 couples will be available for analysis at all time points. Due to the clustered nature of the dyadic data, observations from participants who belong to the same couple will be correlated. In m-PI [name]'s previous study of 190 TW and their male partners, for instance, the average within-couple correlation of sexual risk measurements was $r=.$ 07. Accordingly, we lowered the effective sample size (ESS) input for the power analyses to be $ESS= N/DEFF$, where DEFF is the design effect or variance inflation attributable to using correlated data. DEFF is computed as $1+(M-1)*r$, where M is the number of participants per dyad (i.e., two). Therefore $DEFF=1+(2-1)*.07=1.07$, so $ESS=160/1.07=149$. Assuming, $\alpha=.05$, power=.80, and $ESS=149$, we computed the minimum detectable odds ratio (OR), proportion difference (pdiff), and standardized proportion difference (h) for the proposed time-averaged comparisons, assuming four post-baseline measurements and a wide range of CR-HIV base rates P_0 for levels of risk for TW and their partners seen in the literature.^{4,5,20} Since the within-subject correlation ρ for repeated measures is unknown, we varied it across a wide range from .20 to .80 (see Table 2). The obtained minimum detectable effect size estimates are similar to or smaller than those detected in our pilot study, suggesting that our study is sufficiently powered to test primary Hypothesis 1.

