Original Power Calculations. Originally, our sample size of 100 couples would allow us the statistical power to engage in meaningful comparisons between the two intervention arms. We assumed the 200 participants from 100 couples will be evenly assigned to the intervention arms: 50 couples in intervention and 50 couples in control. Assuming 20% attrition, data from 160 participants (80 couples) would have been available for analysis at all time points (i.e., 3-, 6-, 9, 12-month follow up). Using NCSS PASS, we conducted a series of power calculations to determine the maximum sample size requested to address the primary study aims. We computed the minimum detectable odds ratio (OR), proportion difference (pdiff), and standardized proportion difference (h) across our two study arms for the proposed time-averaged comparisons, assuming four post-baseline measurements and a wide range of base proportions for levels of risk for TW and their partners seen in the literature (i.e., 10%-50%). Since the within-subject correlation ρ for repeated measures is unknown, we varied it across a wide range from .20 to .80. Under these conditions, ORs ranged from 0.17 to 0.56, raw proportion differences ranged from 6.6% to 20.5%, and standardized proportion differences (h) ranged from .27 to .42. **Revised Power Calculations.** We repeated the power analysis approach utilized in our proposal submission. The revised power analysis again assumes $\alpha=0.05$, power=0.80, 4 post-baseline measurements, and baseline reference proportions ranging from 0.10 to 0.50. The within-subject correlation for repeated measures was allowed to vary from 0.20 to 0.80. The N of participants was varied from 100 to 200 to illustrate the potential impact of various sample size reductions on the ranges of minimum detectable effect sizes. Conventional benchmarks for effect size are $h=0.20$ for a small effect size, $h=0.50$ for a medium effect size, and $h=0.80$ for a large effect size. Assuming we reach at least 50% of our goal of recruiting 100 couples, under most circumstances we will still be able to detect a small-to-medium effect size. Even under the least advantageous combination of circumstances (recruiting only 50 couples, baseline reference proportions closer to 10%, and very high correlations between repeated measures), a medium-to-large effect size is still detectable.

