Our Data Safety Monitoring Board (DSMB) reviewed and approved this request on February 14, 2022, and our NIMH sponsor approved the request on July 26, 2022.

11.4 * PARTICIPANT AGE RANGE: Eligible age ranges: (REQUIRED)

- 0-6 years
- 7-12 years
- 13-17 years
- 18-64 years
- 65+

11.5 * STUDY POPULATIONS: Data will be collected from or about the following types of people (check all that apply): (REQUIRED)

- Inpatients
- Outpatients
- Family members or caregivers
- Providers
- People who have a condition but who are not being seen as patients
- Healthy volunteers
- Students
- Staff of UCSF or affiliated institutions
- None of the above

11.6 * SPECIAL SUBJECT GROUPS: Check the populations that may be enrolled: (REQUIRED)

- Children / Minors
- Adult subjects unable to consent for themselves
- Adult subjects unable to consent for themselves (emergency setting)
- Subjects with diminished capacity to consent
- Subjects unable to read, speak or understand English
- Pregnant women
- Fetuses
- Neonates
- Prisoners
- Economically or educationally disadvantaged persons
- None of the above

11.7 INCLUSION CRITERIA: Briefly describe the population(s) that will be involved in this study. Include anyone that data will be collected from or about (e.g. patients, healthy controls, caregivers, providers, administrators, students, parents, family members, etc.):

Inclusion criteria:

1. Age 18 or older;
2. Self-reported primary partnership for at least 3 months;
3. Have had sex with primary partner in the last 6 months;
4. Either partner has had condomless sex with any partner in last 6 months;
5. At least one partner must be a trans woman;
6. Able to provide informed consent;
7. English speaking; and
8. Couples may be HIV-negative concordant, HIV-positive concordant, or HIV serodiscordant.

11.8 EXCLUSION CRITERIA: List any exclusion criteria (e.g. reasons why someone would not be included in the study):

Exclusion criteria:

1. Appears to be psychotic, or otherwise unable to complete Informed Consent procedures.
2. Participation would be unsafe.

11.9 * RESEARCH CONDUCTED ON PATIENT CARE WARDS: Do any study activities take place on any patient care units including inpatient wards, peri- or post-operative care units, operating rooms, or in the Emergency Department at UCSF Health medical facilities: (REQUIRED)

Yes No

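### Baseline CR-HIV is not a named covariate in the primary GEE; fixing it in advance is a cheap improvement whose gain rests on a correlation the documents do not give

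*Combined protocol and SAP*

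**What the plan says.** Section 8.13 of the combined protocol and SAP defines the primary test as a "planned time-averaged comparison of post-baseline measurements of CR-HIV" between arms, by GEE, aimed at a marginal effect. On covariates it says "Couple serostatus will be included as a covariate as required by the stratified randomized design". Relationship length and sociodemographic variables are examples of further covariates that "will be included if they improve QIC". The preliminary-analysis paragraph of the same section adds propensity-score or doubly robust methods, which apply "If the intervention and control groups differ significantly at baseline on one or more covariates". Neither rule names baseline CR-HIV.

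The ingredients of CR-HIV (section 8.11, item 4) are collected at the Enrollment Visit (section 8.9): the survey, viral load for HIV-positive participants, and dried blood spots for recent PrEP users seen in person. The follow-up survey mostly repeats the baseline items.

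The revised power calculation in section 11.3 assumes "4 post-baseline measurements, and baseline reference proportions ranging from 0.10 to 0.50", and adds: "The within-subject correlation for repeated measures was allowed to vary from 0.20 to 0.80". It takes no credit for a baseline measurement and gives no baseline-to-follow-up correlation.

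**The concern.** When the outcome is also measured at baseline, it is usually the strongest candidate covariate. Here it could enter only if the two rules above are read to cover it, and both depend on the data: QIC is computed from the outcome fit, and the imbalance rule needs a significant difference. In a trial of 54 couples two things are at stake: precision, and keeping the covariates of the single alpha-.05 test out of the data.

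How much precision is at stake turns on r_b, the correlation of couple-level baseline CR-HIV with each follow-up value. Three features may lower r_b or use up its value:

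- Entry is restricted by the criterion "Either partner has had condomless sex with any partner in last 6 months".
- Partners are followed individually after a break-up.
- Serostatus, which is built into the CR-HIV algorithm, is already in the model.

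**Working it through.** **1. The plan's own figures.** Inputs from section 11.3: 160 participants after attrition, within-couple correlation .07, four post-baseline visits, alpha .05 (two-sided assumed), power .80, control rates .10 to .50, rho .20 to .80. Effective size = 160/1.07 = 149.5 (stated as 149), or about 74.5 per arm. With VF = (1 + 3 rho)/4,

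n per arm = VF × (1.96 + 0.84)² × [2/(p̄(1 − p̄))] / (ln OR)².

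This returns OR 0.166 to 0.556, differences of 6.6% to 20.4% and h .275 to .419. The plan states 0.17 to 0.56, 6.6% to 20.5% and .27 to .42. The figures reproduce with follow-up data alone.

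**2. What adjustment can do in principle.** VF is .40, .625 and .85 at rho .2, .5 and .8. Adjusting for baseline replaces VF by VF − r_b², so the variance ratio is 1 − r_b²/VF.

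- r_b = rho: 1 − .04/.40 = .90; 1 − .25/.625 = .60; 1 − .64/.85 = .247.
- r_b = rho/2: 1 − .01/.40 = .975; 1 − .0625/.625 = .90; 1 − .16/.85 = .812.

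These ratios ignore the cost of estimating the term, small-sample correction and overlap with serostatus. They are upper guides only.

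**3. How blunt the imbalance rule is.** With 27 couples per arm, a significant baseline gap in CR-HIV, if the rule covers it, needs 1.96 × √(p(1 − p) × 2/27) = .160, .244 and .267 at p = .1, .3 and .5. That is 16, 24 and 27 percentage points.

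**4. Simulation at the planned size.** Set-up: 54 couples, four follow-ups, couple-level binary outcome, logistic GEE with Mancl-DeRouen variance and t reference, serostatus in both models, 3,000 trials per cell, failed fits counted as non-rejections. Assumptions: h = .40 (.50 to .305, .30 to .137), chosen because "Our pilot study found standardized effect sizes ranging from .38 to .42"; serostatus strata of 22, 16 and 16 couples; r_b set on the binary scale. Power without → with baseline CR-HIV, in %, over control rates .3 and .5:

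| Scenario | rho .2 | rho .5 | rho .8 |
|---|---|---|---|
| r_b = rho, no serostatus effect | 59 → 61–63 | 38–40 → 52–57 | 25–27 → 42–59 |
| r_b = rho, serostatus carries half the between-couple variance | 71–73 → 70–72 | 53–59 → 59–68 | 45 → 59 (rate .5 only) |

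The missing cell (rate .3, rho .8) is unreliable: 42–53% of fits failed.

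- r_b = rho/2: −1.7 to +2.3 points over 12 cells; −2.8 to +2.1 with 44 couples (about 20% attrition).
- r_b = 0: a loss of 1.5 to 2.7 points.
- 10% rate: logistic fits failed in 33–99% of trials without the term and 40% to over 99% with it. A linear model of couple means changed by −5 to +1 points.
- Type I error with the term, rates .3 to .5: 1.8–3.8% (GEE); 3.0–4.2% (linear model).

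A smaller simulation (300 trials per cell, 50% vs 30%, 27 couples per arm, no serostatus term, r_b = rho) gave 67 → 69, 48 → 63 and 35 → 74%. The pattern is the same. The larger simulation keeps serostatus in the model, as the plan does, and is the one relied on.

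**The case against.** The strongest reply is that nothing is wrong: the stated contrast is coherent, randomisation protects it, and the section is a brief summary on an IRB form. That stands. A reader might infer bias or an inflated error rate from the omission; nothing in the documents supports that.

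A reader might also take the plan's .20 to .80 as the range of r_b and conclude that up to three quarters of the variance could be removed. The documents do not support this. That range describes repeated measures in a power model of four post-baseline visits. Power thresholds that start from 80% should not be used either, because no simulated cell starts that high and the gain at half-correlation is about zero.

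The opposite inference, that the entry criterion makes every couple a baseline case, also fails. CR-HIV further requires a serodiscordant or unknown-status partner, a 3-month window, and PrEP non-adherence or lack of viral suppression.

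Two further objections stand and shape the fix. First, not every baseline component is sure to pre-date assignment. Section 8.9 allows the viral load to be drawn at an outside laboratory, and section 8.3 makes only the surveys a precondition for randomisation. Second, that the QIC and imbalance rules would cover baseline CR-HIV is an inference from their open wording.

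Finally, the simulated model is a couple-level GEE, not the plan's three-level alternating logistic regression with uncorrected sandwich errors. It tests the model's arm coefficient, not a standardised effect. The power figures are therefore a guide, not a forecast.

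**Conclusion.** The point holds as a worthwhile improvement, with medium confidence; it is not a correction of an error. The pre-specification argument needs no value of r_b. The precision argument does, and is lopsided: small losses if baseline predicts weakly, double-digit gains possible if it predicts about as well as follow-ups predict each other and rho is .5 or more. At rho .2 with r_b equal to it, the simulated change was only about −1 to +4 points. At a 10% base rate precision gives no reason to adjust. These sizes rest on the assumed h of .40, the assumed serostatus mix, couples as the unit of analysis, and control rates of .3 to .5 except where stated.

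**What to change.** In section 8.13:

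1. State arm, couple serostatus and couple-level baseline CR-HIV (section 8.11 algorithm) as the complete covariate set of the primary model. Move QIC-selected covariates and the significance-triggered methods to sensitivity analyses. Keep the serostatus-only contrast as a further sensitivity analysis.
2. Score baseline CR-HIV only from data that pre-date assignment. Do not use a laboratory viral load drawn after assignment; use a result from the previous 30 days, a route section 8.9 already allows, or impute under the plan's multiple imputation.
3. Write one PrEP-adherence scoring rule for remote participants and apply it at baseline and follow-up. Dried blood spots are in-person only, section 9.1 drops hair analysis, and the remote laboratory lists in section 8.9 give no measure for PrEP users.
4. Report the marginal OR and risk difference by standardising over the observed covariates, because the raw coefficient becomes a conditional OR.
5. Name one sparse-data fallback, triggered by a pooled event count set before unblinding. For example, use a linear model of each couple's mean follow-up CR-HIV on the same terms; its arm coefficient is itself a marginal risk difference.

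Cost: no new visits or specimens, but a written scoring rule, a standardisation step, a fallback and extra sensitivity analyses. The term uses one degree of freedom and risks the small power losses given above. Convergence failures rise when CR-HIV is rare or very stable: at rho .8 with r_b = rho and no serostatus effect, from 0 to 9% of fits at rate .5 and from 1.4 to 20% at rate .3.

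### With 54 couples, the primary GEE adds covariates by QIC and names no small-sample correction: simulated type I error averages about 8% if arm is in the search and about 6% if not, against a nominal 5%

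*Combined protocol and SAP*

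**What the plan says.** The primary analysis is in section 8.13, Statistical Methods. It is a GEE comparison of the arms on CR-HIV averaged over the follow-up visits, and alpha "will be set at .05 for this planned comparison".

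- **Clustering.** "The alternating logistic regression (ALR) approach implemented in SAS PROC GENMOD will be used to address the 3-level clustering", and QIC picks the working correlation.
- **Covariates.** Couple serostatus is fixed because randomisation is stratified on it. Beyond that, "Additional relevant covariates such as relationship length, as well as intersectionality criteria and structural drivers" (age, race/ethnicity, poverty and unemployment are given as examples) "will be included if they improve QIC".
- **Standard errors.** The plan relies on Huber-White "standard errors to obtain correct inferences even if the chosen correlation structure remains slightly misspecified". The supplied text names no small-sample correction, t reference or degrees-of-freedom rule.
- **Missing data.** "We will address incomplete data with multiple imputation".

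Section 8.3 sets the trial at 54 couples. Section 11.3 was first built on 100 couples. Its revised calculations rework the detectable effects for fewer couples but do not return to the behaviour of the test.

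**The concern.** The sandwich estimator is justified for many clusters, and here the cluster is the couple. With 54 of them, the uncorrected sandwich tends to be too small, and more so with each covariate parameter added. The five named covariates add up to seven parameters if race/ethnicity has four groups (1 + 1 + 3 + 1 + 1). With intercept, arm and two serostatus terms that makes 11 parameters on 54 couples. QIC is computed from the outcome, so the covariates of the one confirmatory model would also be settled after outcomes are seen.

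At stake is the stated error rate. If the test really rejects about 8% of the time under no effect, that is about 1 false positive in 12 instead of 1 in 20, and a p-value just under .05 would overstate the evidence for the intervention.

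**Working it through.** **The plan's own figures.** ESS = 160/1.07 = 149.5, so about 74.5 per arm. The smallest detectable log odds ratio is

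b = (1.96 + 0.84) × sqrt{ [2/(p̄q̄)] × [(1 + 3ρ)/4] / 74.5 }.

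At a 50% base rate and ρ = .2, p̄ = .429, and b = 2.80 × sqrt(8.17 × 0.40/74.5) = 0.587, an OR of 0.556. At 10% and ρ = .8 the OR is 0.166. These match the stated 0.17 to 0.56. The calculation takes alpha = .05 as given, so it says nothing about whether the test holds that level. That has to be simulated.

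**Inputs from the documents.** 54 couples, 1:1, stratified by three serostatus groups (8.2, 8.3, 11.1); couple-level binary CR-HIV (8.11); four follow-up visits and ρ from .2 to .8 (11.3); base rates .2, .3 and .5, within the 10-50% range of 11.3; race/ethnicity mix from the pilot (8.5).

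**Assumptions not in the documents.** Two-sided test; serostatus mix 50/20/30; relationship length and age normal, poverty 50%, unemployment 40%; candidates unrelated to outcome unless stated; forward search; Wald test; no visit effect.

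**Method.** Logistic GEE with couple as cluster. V = A⁻¹(Σ uᵢuᵢ′)A⁻¹, where A is the model-based information and uᵢ the score of couple i. QIC = −2QL + 2 tr(AV). The Kauermann-Carroll (KC) correction, at couple level, divides each squared residual by (1 − leverage). The t reference has couples minus parameters as degrees of freedom. Outcomes came from a latent-normal model (4,000 runs per cell). The arm-blind rows come from a beta-binomial model (1,000-1,200 runs per cell). The Monte Carlo SE at 8% is sqrt(.08 × .92/4000) = 0.4 point per cell, and 0.9 point at 1,000 runs.

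**Rejection under no effect, 54 couples, nominal 5% (nine cells):**

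| Covariates | Errors | Mean % | Cells % |
|---|---|---|---|
| QIC search, arm in model | uncorrected | 8.3 | 7.5-9.5 |
| QIC search, arm left out | uncorrected | 6.2-6.4 | 4.9-8.7 |
| All five fixed | uncorrected | 8.9 | – |
| Serostatus only | uncorrected | 5.9 | 4.9-6.6 |
| QIC search, arm in model | KC + t | 5.9 | 4.6-7.1 |
| QIC search, arm left out | KC + t | 4.5-4.7 | 3.3-6.5 |
| All five fixed | KC + t | 4.6 | 3.6-5.5 |
| Serostatus only | KC + t | 4.6 | 3.6-5.2 |

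The two arm-left-out means are from two sets of runs, and the cell range is from one of them. Beta-binomial runs of the first row gave means of 8.1-8.4%, with cells from 5.7 to 10.1%.

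**Variants, arm in the search, uncorrected (means).** Couple-level ALR 8.2%; score test 7.4-7.9%; person rows 7.1%; nested ALR with within-couple r = .07, 7.6%; multiple imputation with 20% dropout 7.6%. With 43 couples (54 × 0.8) 9.0-9.7%; prognostic covariates 9.1% (8.2% in the beta-binomial model); seven candidates 9.5%, eight 10.7%. With 100 couples 6.4%, and with 300 couples 5.4%.

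**Where the excess comes from.** Forcing in all five covariates is no better than searching (8.9% against 8.3%), so selection as such is not the cause. Correcting the errors but keeping the arm-in search removes 8.3 − 5.9 = 2.4 of the 3.3 excess points. Dropping to serostatus only, uncorrected, also gives 5.9%, but that removes covariates as well as closing the list. A fixed list of serostatus plus two covariates, uncorrected, leaves 6.6-6.8%. Added parameters and uncorrected errors act together.

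**The case against.** The strongest objection is that section 8.13 does not say whether arm is in the model while QIC chooses covariates. Searching without arm brings the uncorrected rate down to about 6%, and with the correction to about 4.5%, as good as the closed list. This stands. A reader might infer that the plan, followed to the letter, rejects 1 in 12 true nulls. The documents do not support that, because the search model that decides more than half of the excess is unspecified.

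The heading of 8.13 asks the investigators to "Briefly summarize the methods and types of analyses that will be performed". Silence on a correction is therefore not a commitment to uncorrected errors, and citing a fuller document that names one would settle that part. Still, the section is specific about software, ALR, QIC and the sandwich.

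A reader might also take item 5 of section 8.11, "Covariates will include sociodemographic variables such as age, education and income level, employment, race/ethnicity, living situation", as a second candidate list for the primary model. It sits under Instruments and describes what is measured, so it is weak evidence of that. The openness of the list rests on the wording of 8.13.

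Finally, the whole pipeline was never simulated at once. ALR, person-level rows and imputation were varied separately, and QIC choice of the correlation structure and outcome-related dropout were not simulated. This too stands, and it is why the result is given as a range.

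**Conclusion.** The concern holds as a scenario range. At 54 couples, rates of 20-50% and ρ of .2-.8, the primary test has a simulated type I error averaging about 8% (cells about 6-10%) with arm in the QIC search, and about 6% with arm left out. Person-level, nested ALR and imputation variants with arm in average 7.1-7.6%. Losing couples to attrition, prognostic covariates or a longer list mostly give about 9-10%. All of this rests on the assumptions listed, which the documents neither state nor contradict.

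The cause is covariate parameters combined with uncorrected errors on few couples. The evidence does not show that QIC selection alone is at fault, and it does not bear on QIC choice of the working correlation. The switch in 8.13 to propensity or double-robust methods after baseline imbalance, and adjustment for baseline CR-HIV, are outside it too.

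**What to change.** Before outcomes are analysed by arm, specify for the primary model:

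1. A small-sample corrected sandwich clustered on couple, for example Kauermann-Carroll, with a t reference on couples minus parameters. Name the correction: Mancl-DeRouen with t averaged only 3.0-3.4% in the simulations with a closed list of serostatus plus two covariates.
2. Under multiple imputation, pooling of the corrected variances by Rubin's rules.
3. A short closed covariate list: arm, visit, couple serostatus and any covariate named now. QIC covariate selection moves to a sensitivity analysis. If it is kept in the primary model, run it blind to arm and with the corrected errors.

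The simulated rate is then about 4.5% on average, with cells of about 3-6% at rates of 20-50%. For the serostatus-only corrected model, cells are 3.3-5.1% under ALR, 3.5-5.7% under imputation and 3.4-5.7% under nested ALR.

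The cost is plan wording and modest programming if the PROC GENMOD run does not output the correction. At 40% against 20%, apparent power falls from 75.7/56.6/44.5% to 71.0/49.7/37.3% at ρ = .2/.5/.8, a loss of 4.7, 6.9 and 7.2 points, part of which came from the oversized test. Fixing all five covariates costs a further 6-8 points if they are not prognostic, so the list should be short. The corrected test is somewhat conservative at ρ = .8 (down to about 3%). At the 10% rate in section 11.3, even the serostatus-only model failed to fit in 6-34% of runs (all five: 26-73%), and this change does not solve that.
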